## Methods

To study day-to-day variability, each subject's data will be collected on two separate occasions within 7 days.

### Occasion 1

Once arriving to the lab, the subject will answer the following questions by filling in a questionnaire:

1. The subjects age and gender.
2. If the subject is biologically female- Usage of anticonception medication?
3. If the subject is biologically female- Number of days since the first day of the subject's period cycle, alternatively number of years since the subject's most recent period cycle?
4. How many minutes a week does the subject engage in high intensity workout (such as running, football ect)?
5. How many minutes a week does the subject engage in low intensity workout (such as hiking, biking, gardening work ect)?
6. Conformation to not have eaten two hours and not used nicotine, caffeine, or alcohol three hours prior to the experiment.
7. Conformation that the subject do not have a chronic disease such as diabetes, rheumatism ect.

Once the questions are filled in, the subject will receive information about the experiment and gets the opportunity to ask questions, thereafter a consent form is signed. The subject's height and weight will be measured and BMI calculated. The subjects skin type will be determined using the Fitzpatrick scale.

An acclimatization period of 15 minutes begins and the subject will remove socks and lay down. While the subject rests the equipment will be set up. A blood pressure cuff is placed around the upper arm as well as around the ankle. An EPOS-probe is placed on the dorsal side of the foot as well as the volar side of the forearm. A marker pen is used to mark the skin around the probes which enables the probe to be placed on the same location on the next measurement. A vacuum pillow is set up to position the arm and minimize movement artefacts. Once five minutes has passed, the subject's blood pressure and pulse are noted. Thereafter the PSI-X camera is set up and angled to film the plantar side of the foot from about 25 cm. The subject is asked to lay as still as possible during the measurement.

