Once the acclimatization period has passed, the lights in the lab are turned off and the measurement will begin. Firstly, baseline data will be collected as the subject rest for 10 minutes without provocation. Thereafter the blood pressure cuff on the ankle will inflate to 250 mmHg for five minutes whilst data is collected. Lastly data is collected for five minutes after the blood pressure cuff deflates. Thereafter the PSI-X camera is moved and angled to film the forearm from a 25 cm distance. Baseline data will be collected on the arm as the subject rest for 10 minutes without provocation. Thereafter the blood pressure cuff on the upper arm will inflate to 250 mmHg for five minutes whilst data is collected and lastly data is collected for five minutes after the blood pressure cuff deflates. The temperature within the room is noted before and after the measurement.

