## **Occasion 2**

When arriving to the lab, the subject will confirm to not have eaten 2 hours and not have consumed caffeine or alcohol 3 hours prior to the experiment. Thereafter the subject will remove socks and lay down as the acclimatization period begins. A blood pressure cuff is placed around the upper arm as well as around the ankle. The EPOS-probes are placed within the marked skin areas from the previous measurement. A vacuum pillow is set up to position the arm and minimize movement artefacts. Once five minutes has passed, the subject's blood pressure and pulse are noted. Thereafter the PSI-X camera is set up and angled to film the plantar side of the foot from about 25 cm. The subject is asked to lay as still as possible during the measurement.

Once the acclimatization period has passed, the lights in the lab are turned off and the measurement will begin. Firstly, baseline data will be collected as the subject rest for 10 minutes without provocation. Thereafter the blood pressure cuff on the ankle will inflate to 250 mmHg for five minutes whilst data is collected. Lastly data is collected for five minutes after the blood pressure cuff deflates. Thereafter the PSI-X camera is moved and angled to film the forearm from a 25 cm distance. Baseline data will be collected on the arm as the subject rest for 10 minutes without provocation. Thereafter the blood pressure cuff on the upper arm will inflate to 250 mmHg for five minutes whilst data is collected and lastly data is

collected for five minutes after the blood pressure cuff deflates. The temperature within the room is noted before and after the measurement.

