## Statistical analysis of Day-to-day variability

Median values from the baseline data of each measurement will be extracted for all parameters. The maximum value during the post-occlusive reactive hyperemia (PORH) will also be extracted for all parameters. See Table 1 and Table 2 for more details regarding which values will be included in the data analysis.

*Table 1. Values extracted from the EPOS data of each measurement.*

Time period	Conventional perfusion	Speed-resolved-perfusion -Low speed	Speed-resolved-perfusion -Medium speed	Speed-resolved-perfusion -High speed	Oxygen saturation	Vessel diameter	RBC tissue fraction
Baseline of foot (10 minutes)	Median	Median	Median	Median	Median	Median	Median
Occlusion of foot (5 minutes)	No value extracted	No value extracted	No value extracted	No value extracted	No value extracted	No value extracted	No value extracted
PORH in foot (5 minutes)	Peak value	Peak value	Peak value	Peak value	Peak value	Peak value	Peak value
Baseline of arm (10 minutes)	Median	Median	Median	Median	Median	Median	Median
Occlusion of arm (5 minutes)	No value extracted	No value extracted	No value extracted	No value extracted	No value extracted	No value extracted	No value extracted
PORH in arm (5 minutes)	Peak value	Peak value	Peak value	Peak value	Peak value	Peak value	Peak value

*Table 2. Values extracted from the PSI-X camera of each measurement.*

Time period	Conventional perfusion	Speed-resolved-perfusion -Low speed	Speed-resolved-perfusion -Medium speed	Speed-resolved-perfusion -High speed	Oxygen saturation
Baseline of foot (10 minutes)	Median	Median	Median	Median	Median
Occlusion of foot (5 minutes)	No value extracted	No value extracted	No value extracted	No value extracted	No value extracted
PORH in foot (5 minutes)	Peak value	Peak value	Peak value	Peak value	Peak value
Baseline of arm (10 minutes)	Median	Median	Median	Median	Median
Occlusion of arm (5 minutes)	No value extracted	No value extracted	No value extracted	No value extracted	No value extracted
PORH in arm (5 minutes)	Peak value	Peak value	Peak value	Peak value	Peak value

To identify potential sex- and age-related variability, Wilcoxon test will be conducted for non-normally distributed data and t-test for normally distributed data. To compare the data collected from the foot to the arm, Kruskal-Wallis or Anova will be used.

Since multiple comparisons between groups will be conducted, Bonferroni corrections will be done to reduce the risk of Type 1 error.

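### Foot and arm are measured in the same subjects, but the SAP compares them with an independent-samples test (Kruskal-Wallis) or an unspecified ANOVA, and does not say how the two occasions enter

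*SAP*

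**What the plan says.** In the SAP, under Statistical analysis of Day-to-day variability, the whole specification of the site comparison is one sentence: "To compare the data collected from the foot to the arm, Kruskal-Wallis or Anova will be used". No document mentions a paired, repeated-measures, Friedman or mixed-model analysis.

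The protocol's Methods section shows that both sites belong to the same person. For EPOS: "An EPOS-probe is placed on the dorsal side of the foot as well as the volar side of the forearm". For PSI-X, the foot is filmed first, and then in the same session: "Thereafter the PSI-X camera is moved and angled to film the forearm from a 25 cm distance". The session is repeated on a second day: "each subject's data will be collected on two separate occasions within 7 days". At Occasion 2 even the skin location is kept: "The EPOS-probes are placed within the marked skin areas from the previous measurement".

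The SAP extracts values per measurement ("Median values from the baseline data of each measurement will be extracted for all parameters", with post-occlusion peaks handled likewise). It gives no rule for combining the two occasions. On multiplicity it says: "Since multiple comparisons between groups will be conducted, Bonferroni corrections will be done to reduce the risk of Type 1 error". It does not say whether foot versus arm counts among those comparisons.

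**The concern.** For each parameter and period a subject contributes up to 2 sites x 2 occasions = 4 values, and these are not independent. With two sites, Kruskal-Wallis is in effect the Mann-Whitney test, and both require independent samples. Splitting the data into eight site-by-group cells would not cure this, because each subject would still appear in two cells.

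If foot and arm correlate positively within a person, an independent-samples test leaves between-person variance in the error term that pairing would remove. With one value per site, the test is then conservative and can miss real differences. If both occasions were entered as separate independent values, there would be a second error that pulls the other way. As the SAP stands, a reader cannot tell which error applies, or whether the two roughly cancel.

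**Working it through.** **Inputs from the documents.** 4 groups x 12 = 48 subjects, which reproduces the stated total (protocol, Design). The significance level is 0.05 (SAP, Significance level), taken here as two-sided. There are two sites and two occasions per subject. The SAP bases the sample size on custom in the field and gives no effect size, SD or power, so there is no planned power figure to reproduce.

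**Assumptions.** Foot-arm correlation r from 0 to 0.7; same-site between-day correlation (ICC) from 0.5 to 0.9; normal data; equal SDs unless stated; all 48 subjects pooled into one foot-versus-arm comparison.

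**Step 1: one value per site.** The true variance of the difference in site means is 2σ²(1 − r)/48. An independent-samples test uses 2σ²/48. The ratio is 1 − r, so the large-sample type I error is 2[1 − Φ(1.96/√(1 − r))]. At r = 0.5 this is 2[1 − Φ(2.77)] = 0.0056, about 0.6%. Simulation gives the following (power at a true difference of 0.4 SD):

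| r | 0 | 0.3 | 0.5 | 0.7 |
|---|---|---|---|---|
| Type I error, one-way ANOVA | 5.0% | 1.9% | 0.6% | 0.05% |
| Type I error, Kruskal-Wallis | 4.8% | 2.1% | 0.7% | 0.08% |
| Power, one-way ANOVA | 49% | 49% | 49% | 49% |
| Power, paired t | 49% | 63% | 78% | 94% |
| Power, Kruskal-Wallis | 46-47% | 46-47% | 46-47% | 46-47% |
| Power, signed-rank | 46% | 61% | 75% | 93% |

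ANOVA power is flat because 0.4 x √24 = 1.96, which is the critical value itself. That is a feature of this effect size and not a general rule.

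**Step 2: other effect sizes** (5% level, same four values of r).
- 0.5 SD: ANOVA 68 / 71 / 74 / 80%, paired t 67 / 82 / 92 / 99%.
- 0.8 SD: ANOVA 97 / 99 / 99.6 / 99.96%, paired t 97 / 99.6 / 99.98 / 100%.

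**Step 3: unequal SDs.** If one site has twice the SD of the other, ANOVA type I error is 5.0 / 2.6 / 1.4 / 0.4%. Power at 0.4 SD (in root-mean-square SD units) is 49% for ANOVA, against 48 / 60 / 70 / 83% for paired t.

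**Step 4: Bonferroni.** SAP Tables 1 and 2 give (7 + 5) parameters x 2 periods = 24 foot-arm comparisons. If the correction covers exactly these, the level is 0.05/24 = 0.0021. Power at 0.4 SD is then about 12 / 8 / 6 / 3% for ANOVA and 12 / 20 / 33 / 63% for paired t.

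**Step 5: both occasions entered as independent values** (96 per site). Take the foot-arm correlation r to be the same within and across days. The true variance of the difference in means is σ²(1 + ICC − 2r)/48, and the test uses 2σ²/96 = σ²/48. The type I error is 2[1 − Φ(1.96/√(1 + ICC − 2r))]. At ICC 0.7:
- r = 0: 1.96/√1.7 = 1.50, error 13%.
- r = 0.2: 1.96/√1.3 = 1.72, error 9%.
- r = 0.35: 1.96/√1.0 = 1.96, error 5%.
- r = 0.5: 1.96/√0.7 = 2.34, error 2%.

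Over ICC 0.5 to 0.9 the formula gives 11% to 16% at r = 0 and 0.6% to 4% at r = 0.5. In simulation, a paired t-test on the occasion-averaged difference stayed near 5% throughout.

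**The case against.** The strongest reply is that ANOVA may have been meant as repeated measures, or with subject as a blocking factor, either of which would be suitable. For that branch the fault is missing specification and not a definite error. Even a plain one-way ANOVA with one value per site does not exceed 5% error at non-negative correlation. This is fair, but it does not rescue Kruskal-Wallis, which is the named alternative and has no within-subject form. The tests in two adjacent SAP sentences may also have been interchanged: Kruskal-Wallis or ANOVA suits the four independent groups, and a Wilcoxon signed-rank or paired t-test suits foot versus arm. The text does not say so, and it would still need correcting.

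The power loss depends on the effect size. At 0.8 SD and an unadjusted 5% level it almost disappears, though under 0.05/24 a gap of about 85% versus 98.5% remains at r = 0.5. The figures also assume that all 48 subjects are pooled, which the SAP does not state. Compared within one group of 12, power at 0.4 SD and r = 0.5 is about 9% versus 24%. These points limit how far the numbers carry, but independence fails under every reading.

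The inflated error in step 5 needs an analysis step that the SAP never states, together with a low foot-arm correlation. It shows why the use of occasions must be written down. It is not a prediction.

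**Conclusion.** The concern holds and should be fixed before analysis. Kruskal-Wallis is wrong for this comparison as written, the ANOVA is under-specified, and the role of the two occasions is missing.

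With one value per site and positive foot-arm correlation, the cost is a conservative test. It matters for small to moderate differences and little for large ones at an unadjusted 5% level. It is nil at zero correlation and small at 0.1, where power at 0.4 SD is 49% against 52% for the paired test. If the occasions are stacked, the error can fall on either side of 5%. All sizes rest on assumed correlations, SDs and effects. The protocol's Objectives concern day-to-day variability by sex and age, so a foot-arm comparison does not touch the main aim.

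**What to change.** In the SAP, under Statistical analysis of Day-to-day variability, replace the tests named for foot versus arm with one of the following:

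- A paired t-test or Wilcoxon signed-rank test on each subject's foot-minus-arm difference, averaged over the two occasions. State in advance how the choice is made, since the SAP ties its normality rule only to the sex and age comparison. The rule should apply to the differences.
- A linear mixed model per parameter with site, occasion, sex and age group as fixed effects, and random effects for subject and for site within subject. Add site-by-sex and site-by-age terms if the foot-arm difference is to be compared between groups.

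If repeated-measures ANOVA was intended, say so and drop Kruskal-Wallis. State how the two occasions are used, whether all 48 subjects are pooled, and whether Bonferroni covers the foot-arm comparisons and over how many.

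The cost is one or two sentences for the test and the occasions, plus a short line on pooling and multiplicity. The procedures are standard in SPSS, the program that the SAP names, and no new data are needed.

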## Design

Prospective observational study. In the study, four groups will be compared: Men aged 20-30 years, women aged 20-30 years, men aged 50-60 years and women aged 50-60 years. In total 48 participants will be included- 12 from each group.

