## Motivation to the number of study-participants

12 participants in each group (men and women, age 20-30 years or 50-60 years), which adds up to a total of 48 participants, is chosen due to the tradition within the study field. In addition, we do not know if there is a difference among the four groups, which is why we chose a smaller study population.

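### Holm's step-down correction would be a cheap improvement on the single-step Bonferroni named for the group comparisons, although Bonferroni is valid as it stands

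*SAP*

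**What the plan says.** The SAP section Statistical analysis of Day-to-day variability gives the multiplicity rule in one sentence: "Since multiple comparisons between groups will be conducted, Bonferroni corrections will be done to reduce the risk of Type 1 error". It does not say which comparisons form the family or how many there are, and it gives no reason for preferring the single-step method. The Significance level section sets 0.05 without stating sidedness.

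The tests being corrected are described as follows: "Wilcoxon test will be conducted for non-normally distributed data and t-test for normally distributed data". The Protocol's Design section lists the groups ("four groups will be compared: Men aged 20-30 years, women aged 20-30 years, men aged 50-60 years and women aged 50-60 years") and their size ("In total 48 participants will be included- 12 from each group"). The SAP says that this number "is chosen due to the tradition within the study field", that "we do not know if there is a difference among the four groups", and adds "which is why we chose a smaller study population". It states no power target, detectable difference or SD, and it does not plan confidence intervals, adjusted or unadjusted.

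**The concern.** Bonferroni compares every p-value in a family of m with 0.05/m. Holm uses that threshold only for the smallest p-value and relaxes it at each later step, with the same guarantee on family-wise error. In a study that is small by its own description, the single-step rule can miss differences that an equally strict rule would report.

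What is at stake is the pattern of results. The study looks at both sex and age across four groups, so a reader will want to know, for example, whether an age difference appears in men and in women, and not only whether some pair of groups differs. Second and later findings of that kind are the ones on which the two rules can disagree.

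**Working it through.** **The plan's own figure.** 4 groups × 12 = 48, as stated. There is no power calculation to reproduce.

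**Inputs from the documents.** 12 per group; four groups; level 0.05; t-test or Wilcoxon test.

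**Assumptions.** Two-sided tests; t-tests with 12 + 12 − 2 = 22 df; standardised differences of 0.5 to 1.6 SD, because the documents give none.

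**Possible families.**
- All pairs for one parameter: 4 × 3 / 2 = 6.
- Contrasts that differ in sex only or age only: 4.
- All pairs for all extracted values: EPOS 7 parameters × 4 periods = 28, plus PSI-X 5 × 4 = 20, gives 48 values; 48 × 6 = 288.

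**Why Holm never rejects less.** Order the p-values. Holm compares p(i) with 0.05/(m − i + 1) and stops at the first failure. For m = 6 the thresholds are 0.0083, 0.0100, 0.0125, 0.0167, 0.0250 and 0.0500; Bonferroni uses 0.0083 throughout. Each Holm threshold is at least 0.05/m, so every Bonferroni rejection is also a Holm rejection. The argument uses only p-values, so it covers Wilcoxon tests and correlated parameters as well. Step one is identical in both, so the chance of any rejection is the same.

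**Exact check of Bonferroni.** The noncentrality is d√(12/2) = d√6. At d = 1.2 this is 2.94, and power at level 0.05/6 with 22 df is 0.53, which agrees with the simulation below.

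**Simulation.** 4 × 12, six pairwise t-tests, 40,000 runs per setting; average power per true comparison:

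| Assumed effect | Bonferroni | Holm |
|---|---|---|
| One factor, 0.5 SD | 0.066 | 0.071 |
| One factor, 0.8 SD | 0.203 | 0.223 |
| One factor, 1.0 SD | 0.355 | 0.393 |
| One factor, 1.2 SD | 0.530 | 0.584 |
| One factor, 1.5 SD | 0.77 | 0.83 |
| Sex and age, both 1.2 SD | 0.622 | 0.707 |

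- All four true one-factor differences are found in 19% of studies with Bonferroni and 29% with Holm at 1.2 SD, and in 48% and 62% at 1.5 SD.
- At least one rejection, one factor at 1.2 SD: 0.858 with either method.
- Family-wise error: 0.041 for both when no groups differ; 0.016 and 0.029 with one factor at 1.2 SD.

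With only the four single-factor contrasts, average power goes from 0.249 to 0.259 (one factor, 0.8 SD), 0.595 to 0.623 (one factor, 1.2 SD) and 0.592 to 0.709 (both factors, 1.2 SD).

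**One family of 288.** Tests taken as independent, 1,500 runs, half the nulls false: 0.019 to 0.019 at 0.8 SD, 0.104 to 0.107 at 1.2 SD, 0.328 to 0.351 at 1.6 SD. If every null is false, at 1.6 SD: 0.328 to 0.388.

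**Effect of the family itself.** Bonferroni power per test at 1.2 SD is 0.80, 0.59, 0.53, 0.25 and 0.10 for m = 1, 4, 6, 48 and 288.

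**The case against.** The strongest reply is that nothing in the plan is wrong. Bonferroni does what the SAP wants of it, and no power claim or confirmatory decision in the documents is defeated by it. That stands. Being outperformed is also a weak test of error: for all pairwise comparisons Holm can itself be improved on by Shaffer's procedure, which uses the logical links between the hypotheses.

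The gain can also look larger than it is. At effects up to 1 SD it is about 0.5 to 4 points, and the two rules reach different decisions in only 2% of studies at 0.5 SD and 8% at 0.8 SD. The measure of finding all four differences is the most favourable one, and the plan does not require it. This too stands, and it limits the weight of the point.

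A reader might infer that power is being given away for nothing. The documents do not support that. Bonferroni has one fixed threshold and simple matching simultaneous intervals, which Holm does not provide as directly. The answer is only that the SAP commits to no such intervals, so nothing now planned would be lost.

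A reader might also infer that an effect of a single factor is where Holm helps most. It is not: with both factors at 1.2 SD the gain is 0.707 − 0.622 = 0.085, against 0.584 − 0.530 = 0.054 with one.

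Finally, the undefined family matters far more than the choice between the two rules: 0.53 against 0.10 at 1.2 SD for m = 6 and m = 288. That is correct, and Holm does not resolve it. It is a separate gap and does not weaken the comparison, because Holm rejects at least as much for any m.

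**Conclusion.** The point holds as an optional, low-cost improvement. For whatever family is adopted, Holm gives the same family-wise control and never fewer rejections. With six comparisons per parameter the gain in average power is about 2 points at 0.8 SD, 5 at 1.2 SD and 6 at 1.5 SD for one factor, and 8 to 9 points if both factors act at 1.2 SD. In a single family of 288 with half the nulls false it is 0 to 2 points.

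That Holm never rejects less needs no assumption about effects or correlation. The sizes do: they rest on assumed effects, two-sided t-tests and, for the large family, independent tests. Real parameters will be correlated and some will be analysed by rank tests, so the figures are indicative.

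**What to change.** In the SAP's Day-to-day variability section, name a Holm step-down correction at family-wise 0.05 in place of Bonferroni. Suggested content: the m p-values of the family are ordered from smallest to largest and compared with 0.05/m, 0.05/(m − 1), …, 0.05, stopping at the first failure; Holm-adjusted p-values are reported.

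Leave m general in the wording and have the sponsor define the family before analysis. Writing in 0.05/6 would settle a question that the SAP leaves open. The rule should also be fixed before the data are analysed, since choosing it afterwards would be open to question.

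The cost is one line of text and a ranking of the p-values from SPSS, with no new data or participants. The downside is that matching simultaneous confidence intervals are less simple. If unadjusted 95% intervals are shown beside Holm-adjusted p-values, the two can disagree, and the report should say so.
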